## 9 STATISTICAL CONSIDERATIONS

### 9.1 STATISTICAL HYPOTHESES

Outcome measures include 1-13 month post-procedure rates of cardiac death and myocardial infarction. This single-arm prospective design will compare rates on the dependent variables following

Boston Scientific IVUS-guided SYNERGY™ Stent implantations with standard of care rates in the target population. The null and alternative hypotheses are as follows:

$$H_0 = p = p_0$$

The null hypothesis states that there is no difference on myocardial infarction or cardiac death rates.

$$H_1: p < p_0$$

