## 9.2 THE ALTERNATIVE HYPOTHESIS STATES THAT PATIENTS UNDERGOING SYNIVUS-DAPT TREATMENT WILL HAVE LOWER RATES OF MYOCARDIAL INFARCTION OR CARDIAC DEATH. SAMPLE SIZE DETERMINATION

An a priori power analysis was conducted for a one-sample binomial test with an alpha of .05 (one-tailed), beta of .05, constant proportion ( $p$ ) of .031, and assumed primary endpoint proportion of 0.0047 resulting in a needed sample size of 231.

The consideration of historical data on timing and incidence of myocardial infarction and stent thrombosis from published meta-analysis and related literature, the SCAAR registry and ACS subsets (De Luca, Dirksen, Spaulding, et al, 2012; Ellis, Colombo, Grube, et al, 2007; Palmerini, Biondi-Zocca, Riva, et al, 2012; Palmerini, Kirtane, Serruys, et al, 2012; SCAAR registry and ACS subset, 2016). Historic rates at 1-year follow up for ST showed variability ranging from 0.3 to 5.3%. Rates of MI range from 1.9 to 8.8%. A time-to-event bivariate exponential distribution function was used to determine criteria for sample sizes based on a 95% power determination resulting in a historic rate determination of 3.1%. Patients lost to follow-up will not be included in the final analysis, and additional patients will be recruited for study participation to reach the needed sample of 231.

The FDA has approved an initial phase of the investigation for 100 U.S patients. Accordingly, the sample size of N=100 for the initial phase is not statically based. Should approvals for study continuation be granted, the total sample size for subsequent phases will remain at 231, inclusive of subjects enrolled on this initial phase.

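### The 3.1% benchmark is not shown to be the standard of care rate that Section 9.1 promises to compare with, so rejecting H0 supports only a rate below 3.1%

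*Combined protocol and SAP*

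**What the plan says.** Section 9.1 sets H0: p = p0 against H1: p < p0 and says the comparison is with "standard of care rates in the target population". The Section 9.2 heading carries the alternative: treated patients "WILL HAVE LOWER RATES OF MYOCARDIAL INFARCTION OR CARDIAC DEATH".

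Section 9.2 supplies the only value of p0 in the document, 0.031. It reports considering "historical data on timing and incidence of myocardial infarction and stent thrombosis from published meta-analysis and related literature, the SCAAR registry and ACS subsets". It gives two ranges, in per cent: "Historic rates at 1-year follow up for ST showed variability ranging from 0.3 to 5.3" and "Rates of MI range from 1.9 to 8.8". As to method, it states that "A time-to-event bivariate exponential distribution function was used to determine criteria for sample sizes". The benchmark is presented as the outcome of that step, which is described as "based on a 95% power determination resulting in a historic rate determination of 3.1" (per cent).

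The primary endpoint (Sections 1.1 and 3) is cardiac death or MI by the SCAI definition, from month 1 to month 13, in patients eligible to stop DAPT at 30 days. Section 5.1 requires every patient to be at high bleeding risk. Section 5.2 excludes STEMI and NSTEMI as the indication for the index procedure. Section 7.1 bars P2Y12 cessation after a first-month MI or stent thrombosis, among other events.

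The currently approved phase is 100 patients, and "the sample size of N=100 for the initial phase is not statically based" (the document's wording; evidently statistically).

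**The concern.** There is no control arm, so any comparative statement rests entirely on p0. A binomial test against 3.1% is a valid test of whether the rate is below 3.1%. It becomes a test against standard of care only if 3.1% is the standard of care rate for the same endpoint, window and population. The text does not show that on any of the three, and no other section supplies the missing rate. Section 3 aligns the endpoints and timing with another short-DAPT trial but quotes no rate from it.

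At stake is the claim handed on to the larger studies this pilot is meant to inform. Followed as written, the plan would let a rejection be reported as better than standard of care.

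**Working it through.** **1. The plan's sample size reproduces.** Inputs from Section 9.2: one-sided alpha 0.05, beta 0.05, p0 = 0.031, p1 = 0.0047. By the arcsine formula, n = [(1.645 + 1.645) / (2·asin√0.031 − 2·asin√0.0047)]² = (3.290 / 0.2168)² = 230.3, so 231. The arithmetic that follows from 3.1% is not in question.

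**2. The 3.1% itself cannot be reproduced.** Section 9.2 gives source ranges and a model name, but not the values or weights entered. A historic rate is normally an input to a power calculation, whereas here it is described as a result of one.

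**3. Benchmark against promised comparator.**

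| | Promised (9.1, with 1.1, 5.1, 5.2) | Shown in 9.2 |
|---|---|---|
| Endpoint | cardiac death or MI | MI and stent thrombosis separately; no cardiac death or composite rate |
| Window | month 1 to 13, eligible patients | 1 year for stent thrombosis, none stated for MI; nothing landmarked at month 1 |
| Population | high bleeding risk; no STEMI or NSTEMI indication | general literature, a registry and ACS subsets; none labelled high bleeding risk |

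**4. Direction.** If cardiac death or high bleeding risk is missing from the sources, p0 is too low and the test is conservative. If first-month events or higher-risk ACS patients are included, p0 is too high and the test is too easy. The documents do not settle which dominates.

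**5. The decision rule (derived; the plan does not state it).** With X ~ Bin(231, 0.031), P(X ≤ 2) = 0.0247 and P(X ≤ 3) = 0.0707. H0 is rejected at 2 or fewer events, whether alpha is 0.05 or the final 0.0492 of Section 9.4.4. Power at 0.0047 is P(X ≤ 2) = 0.904.

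**6. Illustration.** The matched rate is not in the documents, so I assume values within the stated MI range of 1.9% to 8.8%. The table gives the chance that a strategy whose true rate equals the comparator is declared better.

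| Assumed comparator | Cut-off 2 events | Cut-off 1 event |
|---|---|---|
| 1.9% | 18.4% | 6.5% |
| 2.5% | 7.0% | 2.0% |
| 3.1% | 2.5% | 0.6% |
| 4.0% | 0.5% | 0.1% |

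For example, at 1.9% P(X ≤ 2) = 0.0119 + 0.0532 + 0.1186 = 0.1837. With a cut-off of 2, the probability reaches 5% at a comparator of about 2.7%; above that the rule is conservative.

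The second column assumes 231 evaluable patients in the primary set and no Bonferroni reduction. The cut-off could be 1 event in two ways. Section 9.4.2 applies alpha/m to multiple tests: 0.0492/2 = 0.0246 is just below 0.02466, and 0.05/3 = 0.0167 is clearly below it. Alternatively, if 231 is enrolment and only about 152 to 200 patients are eligible to stop DAPT, the exact cut-off at 0.05 is again 1.

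**7. What a bound would show.** Exact (Clopper-Pearson) one-sided 95% upper limits are 1.3%, 2.0%, 2.7% and 3.3% for 0, 1, 2 and 3 events in 231, and 3.0% and 4.7% for 0 and 1 event in 100.

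**The case against.** The sponsor can fairly say several things.

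- **The study is a pilot.** Sections 1.1 and 4.1 hypothesise only that rates will be low and hypothesis-generating, and the 231-patient test runs only if further approval is given. This stands and limits the consequence. But Sections 9.1, 9.2 and 9.4.2 still plan a powered comparative test.
- **Every single-arm trial with a fixed benchmark supports only a rate below that benchmark.** True. The point here is that Section 9.1 says more than that.
- **The cited sources may hold the missing rates.** They may. This is a gap in the text on endpoint, window and population alike, not evidence that the sources lack them. No weight is stated for the ACS subsets, and unstable angina is not excluded, so that mismatch may be partial.
- **Timing was considered.** Under an exponential model with constant hazard, 12-month risk from month 1 among event-free patients equals 12-month risk from time zero. This partly answers the window point, but the fitted values are not given.
- **Most of the MI range is harmless.** Within the same patients and window, the composite cannot be below MI alone, so low comparators apply only if landmarking or lower-risk patients pull the rate down. This stands. The width of a literature range also says nothing about how likely each value is.

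A reader might infer that 3.1% is wrong, or that the trial carries an 18% false-positive risk. The documents support neither: 3.1% lies inside the stated MI range, and 18.4% needs a comparator at the bottom of that range together with the 2-event cut-off.

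**Conclusion.** The point holds as a limit on the conclusion. The 3.1% benchmark is unsupported as the standard of care rate for month 1 to 13 cardiac death or MI in high-bleeding-risk patients, and rejecting H0 supports only a rate below 3.1%. The direction of any error is unknown. The test would be too easy only if the matched rate were under about 2.7%, assuming 231 evaluable patients, no Bonferroni reduction and a cut-off of 2 events; a cut-off of 1 event shrinks that risk further. It should be fixed because the correction is cheap and changes what the trial may claim. It is no more serious than that, given the pilot status and an approved phase of 100 patients.

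**What to change.** 1. In Section 9.1 and the Section 9.2 heading, call 3.1% a fixed performance goal and limit the conclusion to a rate below 3.1%.
2. In Section 9.4.2, report the month 1 to 13 rate of cardiac death or MI with its exact one-sided 95% upper bound beside the binomial test. Do the same if the trial stops at the initial phase. Readers can then set the bound against any benchmark they accept.

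Cost: protocol wording and one reported bound, no added patients, and a weaker headline claim.

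Separately, as a documentation request, state in Section 9.2 the values and weights entered in the bivariate exponential model.

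Replacing p0 with a matched rate is optional and must be priced on its own. At N = 231, exact one-sided 0.05 and p1 = 0.0047, power would be 34% at p0 = 1.9% (cut-off 0 events), 70% at 2.5% (cut-off 1), 90% at 3.1% (cut-off 2) and 99.5% at 4.0% (cut-off 4). At the low end, keeping 95% power would need more patients: about 556 at 1.9% by the normal approximation.

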## 1 PROTOCOL SUMMARY

### 1.1 SYNOPSIS

Title:	SYNERGY™ Stent System Implantation with mandatory Intra-Vascular Ultra-Sound Guidance to Examine the Safety of Cessation of Dual Anti-Platelet Therapy in High Bleeding Risk Patients One Month (SYNIVUS-DAPT)
Study Description:	This is a prospective multicenter single-arm study designed to characterize the safety of 1 month of dual antiplatelet therapy (DAPT) in a patient population who are at increased risk for bleeding who are undergoing iLab IVUS-guided percutaneous coronary intervention (PCI) with a SYNERGY Everolimus-Eluting Platinum Chromium Coronary Stent System (SYNERGY™ Stent System). We hypothesize that the 1 to 13 month rates of Cardiac Death or Myocardial Infarction (SCAI definition), and Stent thrombosis after Boston Scientific IVUS-guided SYNERGY™ Stents implantation will be low and provide key hypothesis generating information to inform future larger-scale clinical studies
Objectives:	Primary Objectives: To determine the safety of 1-month DAPT in a High Bleeding Risk (HBR) patient population who are undergoing SYNERGY™ stent implantation.
Endpoints:	Primary Endpoint: 

• Rate of cardiac death or myocardial infarction (SCAI definition) from 1 to 13 months post-index procedure in the “as treated” (eligible for 30 day DAPT cessation) population.

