**Angiographic Exclusion Criteria**

[figure not shown]
1. Target lesion(s) is located within a saphenous vein graft or an arterial graft
2. TIMI flow 0 (total occlusion)
3. Target lesion(s) is located in the left main

4. Potential Target lesion(s) that involve a complex bifurcation (i.e. bifurcation lesion requiring treatment with more than one stent)
5. Thrombus, or possible thrombus, present in the target vessel (by visual estimate)
6. Patients requiring a treatment of more than two native epicardial vessels
7. More than three lesions in two epicardial vessels unless they can be covered by one stent.
8. In-stent restenosis of target lesion
9. Treatment of non-target lesions or lesions not treated with a Synergy™ stent
10. Subject who did not receive Boston Scientific IVUS guided stent implantation and assessment
11. Any target lesion that has not been post dilated and has not had post dilatation IVUS
12. Patients who do not meet the following IVUS success criteria:
  - Target lesion(s) in which the stent cross sectional area is less than the distal reference cross sectional area and additional post-dilatation is not performed, followed by repeat IVUS.

\*\* Note: If the IVUS criteria is not met after the 2nd post dilatation the patient is excluded

Phase	Pilot
Description of Sites/Facilities Enrolling Participants:	The study will be conducted at HonorHealth System within the Phoenix, Arizona metropolitan area, and two institutions outside of the HonorHealth System. All Institutions within the HonorHealth system will collectively be considered a single “site”. All sites have recognized expertise with Boston Scientific IVUS guided stent implantation and will use IVUS to perform the procedures. The study will not be conducted outside the United States and its territories. Additional sites may be added pending enrollment rates.
Description of Study Intervention:	This is a study designed to follow patients whom have received IVUS-guided Implantation of the SYNERGY™ Stents and discontinued DAPT at 1 month.
Study Duration:	24 Months
Participant Duration:	13 Months
Total Number of Patients:	231

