#### 6.4 STUDY INTERVENTION COMPLIANCE

Compliance to DAPT regimen will be ascertained at the 1-month follow-up visit and will be used to determine if the subject is eligible for discontinuation of P2Y12 inhibitor. During the 1-month follow-up visit, the subject will also be asked about any significant interruptions (greater than 3 days) in the prescribed index procedure.

Follow up at 30 days post DAPT cessation either by phone or clinic visit to assess angina status and targeted endpoints.

Note: All enrolled subjects who receive a SYNERGY™ Stents must be followed at all milestones through 13-months, regardless of eligibility to discontinue DAPT.

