### 7 STUDY INTERVENTION DISCONTINUATION AND PARTICIPANT DISCONTINUATION/WITHDRAWAL

#### 7.1 DISCONTINUATION OF STUDY PARTICIPATION

Subjects should not discontinue P2Y12 inhibitor (the patient will remain in the study until 13 months unless consent to participate is withdrawn) at 1 month if any of the following criteria are met:

- Subject experiences a stroke, MI, PCI, CABG and/or stent thrombosis, during the 1 month period following the index procedure
- Subject is non-compliant with DAPT regimen during the 1 month period following the index procedure. Non-compliant is defined as: DAPT interruption for at least 3 days.
- Subject judged to have another condition rendering them inappropriate for discontinuation from P2Y12 inhibitor at 1 month.

An investigator may discontinue or withdraw a participant from the study if:

- Pregnancy occurs
- Significant study non-compliance beyond DAPT compliance issues

- Continued participation in the study would not be in the best interest of the participant due to other conditions
- The participant is unwilling or unable to discontinue DAPT within 7 days after 30-day post-procedure visit
- Other unforeseen reason

Additionally, participants may withdraw from participation in the study at any time upon their own discretion and a request to the site.

The reason for participant discontinuation or withdrawal from the study will be recorded on Case Report Form (CRF). Subjects who sign the informed consent form but screen fail due to inclusion or exclusion criteria requirements will be replaced.

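### The 231 is sized on the cessation-eligible primary set but also used as total enrolment, with no allowance for patients barred from stopping P2Y12 at day 30

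*Combined protocol and SAP*

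**What the plan says.** The primary endpoint (sections 1.1 and 3) is the rate of cardiac death or MI from 1 to 13 months in the as-treated set, glossed as "eligible for 30 day DAPT cessation) population". The same rate in everyone enrolled is listed as secondary.

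Section 9.2 sizes the trial on that endpoint: a "one-sample binomial test with an alpha of .05 (one-tailed), beta of .05", with an "assumed primary endpoint proportion of 0.0047 resulting in a needed sample size of 231". It then fixes recruitment at the same figure: "the total sample size for subsequent phases will remain at 231, inclusive of subjects enrolled on this initial phase". The synopsis repeats it: "Total Number of Patients: 231".

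Section 7.1 lists reasons not to stop the P2Y12 inhibitor at 1 month: stroke, MI, PCI, CABG or stent thrombosis in the first month, a DAPT interruption of 3 days or more, or another condition judged to rule it out. These patients remain in the study. Section 6.4 says that all enrolled recipients of the stent "must be followed at all milestones through 13-months, regardless of eligibility to discontinue DAPT".

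Replacement is described for two groups. Section 7.1: "Subjects who sign the informed consent form but screen fail due to inclusion or exclusion criteria requirements will be replaced". Section 9.2 adds recruitment to make up for patients lost to follow-up. Section 9.3 names only an intention-to-treat dataset of all participants and defines no cessation-eligible set.

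**The concern.** One number does two jobs. It is the size required in a subset and also the size of the whole enrolled group. A patient barred from stopping at day 30 is neither a screen failure nor lost to follow-up, so that patient occupies one of the 231 places without entering the primary analysis. Section 9.2 allows for loss to follow-up but not for this loss, which the primary population builds in.

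The test decides on a handful of events. A shortfall can therefore lower the rejection limit by a whole event and sharply reduce the chance of a conclusive primary result, while the plan still reports a beta of .05.

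**Working it through.** **Inputs.** Null rate p0 = .031 (9.2: "resulting in a historic rate determination of 3.1" per cent); assumed rate p1 = .0047; one-sided alpha .05 and beta .05 (9.2); final-analysis alpha .0492 after the interim (9.4.4); exact binomial test (9.4.2). The share ineligible at day 30, d, is not in the documents and is assumed to lie between 5% and 20%.

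**Step 1: reproduce 231.** The arcsine formula is n = [(z.95 + z.95) / (2·asin√p0 − 2·asin√p1)]². With z.95 = 1.645, this is [3.290 / (.3540 − .1372)]² = 230.3, which rounds up to 231. The score approximation gives 228.5, or 229. The plan's figure is reproduced, and it contains no term for ineligible patients.

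**Step 2: exact test at 231.** Reject if X ≤ c, where c is the largest count with P(X ≤ c | n, p0) ≤ alpha. At n = 231:
- P(X ≤ 2 | .031) = .0247 and P(X ≤ 3 | .031) = .0707, so c = 2.
- Power = P(X ≤ 2 | .0047) = .337 + .367 + .200 = .904.

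The exact test therefore has 90.4% power with nobody ineligible. Under the score approximation power is 95.3% at 231 and falls below 95% once fewer than 229 are eligible, that is, at 3 ineligible patients (about 1%).

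**Step 3: remove ineligible patients** (alpha .0492, exact test).

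| Eligible n | Ineligible | c | P(X ≤ c), p0 | Power |
|---|---|---|---|---|
| 231 | 0% | 2 | .0247 | 90.4% |
| 219 | 5% | 2 | .0328 | 91.5% |
| 208 | 10% | 2 | .0425 | 92.4% |
| 202 | 12.6% | 2 | .0488 | 92.9% |
| 201 | 13.0% | 1 | .0133 | 75.6% |
| 196 | 15% | 1 | .0152 | 76.5% |
| 185 | 20% | 1 | .0204 | 78.4% |

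At n = 201, P(X ≤ 2 | .031) = .0499. This exceeds .0492, so c drops to 1; at alpha .05 it would still be 2, and the drop comes at n = 200 (75.8%). Within a fixed c, power rises slightly as n falls, because the same count is allowed in fewer patients.

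**Step 4: the eligible number is itself random.** Averaging the exact power over m ~ Binomial(231, 1 − d), that is Σ P(m)·power(m), gives 91.4% at d = 5%, 91.0% at 10%, 79.5% at 15% and 78.4% at 20% (alpha .0492).

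**The case against.** The strongest reply is that section 9.3 analyses all participants. If that set governs the primary test, day-30 ineligibility removes nobody and the shortfall does not arise. But 1.1 and 3 make the cessation-eligible set primary and the all-enrolled set secondary, so 9.3 is in conflict with them rather than an answer to them.

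A second reply is that nothing says ineligible patients will not be replaced. That is correct. A reader might infer that they are not replaced and that the primary set cannot reach 231. Both go further than the text: the first is read from silence, and the second needs at least one ineligible patient, which the 7.1 list makes very likely but no stated rate confirms. The synopsis also speaks of about 100 evaluable patients without defining the term. What stands is that replacement is stated for two other groups only and that the total is said to stay at 231.

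Third, up to 12.6% ineligible costs no power under the exact test. That also stands. A reader might infer that the stated power fails at about 13% ineligible. It does not: 95% is already missed at 0% under the exact test and lost at about 1% under the approximation. Thirteen per cent is only where the limit drops from 2 events to 1, and that point depends on alpha. Section 9.4.2 also applies a Bonferroni correction without giving the number of tests. If it were two, alpha would be .05/2 = .025; 231 just allows 2 events (.0247) and 230 does not (.0253).

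Finally, a reader might extend the argument to the first 100 patients. Section 9.2 says that number has no statistical basis, so no power claim attaches to that phase.

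**Conclusion.** The concern holds in this form: 231 is the required size of the cessation-eligible set, it is also the enrolment total, and no allowance or replacement rule covers patients barred from stopping at day 30. Any such patient leaves the primary set short of its planned size.

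The stated 95% power is not what the named test delivers. It is 90.4% at 231, 90-93% down to 202 eligible, and about 76% just below that, rising to 78% at 185. If 5-10% are ineligible the consequence is small (91-92%). At 15-20% the chance of missing a true rate of 0.47% is about 22-24%, against the 5% stated.

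This rests on the plan's p0 and p1, an exact one-sided test at .0492, 1.1 and 3 governing the primary population, and an assumed ineligibility rate. It counts this source of loss only. Section 9.4.2 also drops nonadherent patients and missing data, which would reduce the set further.

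**What to change.** 1. In 9.3, name the cessation-eligible set as the primary analysis set and intention-to-treat as secondary, in line with 1.1 and 3.
2. In 1.1 and 9.2, state that 231 counts enrolled patients with follow-up, after replacement of screen failures and patients lost to follow-up, and not cessation-eligible patients. Calling 231 simply the number enrolled would clash with the top-up already in 9.2.
3. In 9.2, replace the 95% power with the exact rejection count and power at the expected eligible size for a stated ineligibility rate. For example, 10% gives n = 208, at most 2 events, 92%; 15% gives n = 196, at most 1 event, 76%.
4. State that the rejection count is set from the actual eligible number before outcomes are analysed. Eligibility is settled at the last day-30 visit, so this is feasible.

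The cost is wording in three sections and a less favourable stated power. No added enrolment is needed. Securing 231 eligible patients would instead take 231/(1 − d) enrolled, or 257 at 10%, and would still give only 90.4% under the exact test.
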